## **5.0 Study Design**

1. This study will be a single-center, controlled, randomized, double-blind (provider and subject), 2 treatment, 1 period, parallel study to determine the efficacy of buffered 2% Lidocaine w/ 1:100k epi, 3% Carbocaine and 4% Articaine with 1:100k epi, on the time of efficacy and ultimate profoundness of pulpal anesthesia in mandibular molars diagnosed with symptomatic irreversible pulpitis compared to traditional unbuffered 2% Lidocaine w/ 1:100k epi, 3 % Carbocaine and 4% Articaine with 1:100k epi. An electronic pulp tester (EPT) assesses the tooth's ability to feel sensation, with a reading of 80 showing the tooth is adequately anesthetized.

## 6.0 Enrollment/Randomization

Potential research subjects will be pooled from patients scheduled to receive an endodontic evaluation and/or clinical treatment in the Graduate Endodontic clinic at Indiana University School of Dentistry. There are currently 7 endodontic residents enrolled in the graduate program who will be eligible to screen patients presenting to the graduate clinic for elective, urgent, or emergency endodontic treatment. If an endodontic resident other than the student researcher ([name]) diagnoses their respective patient's mandibular molar with symptomatic irreversible pulpitis, and all other inclusion/exclusion criteria are respected, then the student researcher will be eligible to further evaluate the patient and potentially include them in the study.

The study biostatistician will provide a two-product randomization scheme which will randomize each subject on the order of their entry into the study. Subjects will be randomized equally to the two treatments using a block randomization, participants receiving multiple root canal procedures will be treated as a single subject. 30 subjects per treatment will be enrolled. The randomization scheme will be provided to clinic assistants [name] and [name]. They will prepare each anesthetic solution behind closed doors and provide each carpule to the

[figure not shown]
researcher at every appointment. The stopper of every carpule, regardless of experimental group, will be punctured to remove bias. The study subject will be blinded to treatment assignment.

## 7.0 Study Procedures

### Single Visit: Screening and Study procedure

1. Review medical history (about 3-5 minutes)
  - a. If previously on file, the patient will need to verbally confirm all forms are accurate
  - b. If the patient is new to IUSD, then the proper medical history intake form will be completed and confirmed by the patient, as per standard of care
  - c. Participants will be explained what an analgesic is, and will confirm they have not taken any within 6 hours prior to study participation
2. Customary sensibility testing, specifically cold and Electric Pulp Testing (EPT), will be completed to ensure a diagnosis of symptomatic irreversible pulpitis in a mandibular molar specifically on the same day that the warranted endodontic treatment is to be rendered (about 5-10 minutes) as per standard of care.
  - a. Prospective study participants will be given brief instructions on cold and EPT usage/expectations
  - b. A vital, asymptomatic, contralateral posterior tooth (ideally molar) will undergo cold and EPT testing prior to administering anesthesia to serve as an internal control
  - c. The pulpal diagnosis will be primarily confirmed using Endo-Ice
3. Review inclusion/exclusion criteria to ensure that the subject qualifies to continue with the study (about 3 minutes)
4. Perform consenting procedures for both the Non-surgical Root Canal Therapy (NSRCT) and the research study (about 5-10 minutes)
  - a. Study participants will receive a concise explanation regarding the nature of the 2 possible anesthetic formulations and the EPT testing intervals that are expected to follow. Participants will be explicitly notified that the anesthetic formulation will not affect the overall prognosis of the endodontic treatment needing to be rendered. Once profound anesthesia is confirmed, the NSRCT will proceed as usual and customary.
5. Randomize the subject to the type of anesthetic formulation (about 5 minutes)
6. Apply topical benzocaine jelly after thoroughly drying the tissues surrounding the Inferior Alveolar Nerve Block (IANB) injection site and the buccal vestibule of the tooth to be treated (about 1 minute), as per standard of care
7. Administer **1 carpule** (1.8mL) of the previously determined formulation of 2% Lidocaine w/ 1:100k epi and 1 carpule of 3% Carbocaine plane via IANB, followed by 0.5 carpules (0.9mL) of 4% Septocaine with 1:100k epi via buccal infiltration and 0.5 carpules of 4% Septocaine with 1:100k epi via lingual infiltration (about 3 minutes)
8. Using a stopwatch, the student researcher will wait 3 minutes after administering anesthesia and then obtain the 2nd EPT reading on the tooth being treated, as well as assessing soft tissue anesthesia of the respective side of the mandible

- a. EPT=80 (maximum stimulation) without pulpal or soft tissue sensations indicates profound pulpal anesthesia and the endodontic access may be initiated
- b. EPT $\neq$ 80 with pulpal and/or soft tissue sensations indicates a need to wait additional time
9. Retest the tooth being treated using EPT at 2-minute intervals until EPT=80 or when 15 minutes have passed
  - a. Participants who did not demonstrate total soft tissue and/or pulpal anesthesia within 15 minutes will be categorized as a failure (lack of anesthetic profoundness), with time to anesthesia censored at 15 minutes. No additional study outcomes will be collected from the patients, who will be withdrawn from the study, and further managed according to the best clinical practice (additional block/supplementary injections) so that the endodontic treatment may continue appropriately
10. Patients who indicate any pain (excluding pressure) elicited from the tooth undergoing treatment upon endodontic access or a complete pulpotomy (after initially confirming pulpal anesthesia with the EPT) will also be categorized as a failure (lack of anesthetic profoundness), withdrawn from the study, and appropriately managed as previously described.
  - a. Visual Analog Scales (VAS) shown below will be used to report the patient's perceived discomfort at the end of treatment.

11. The student researcher will chart the data for each uniquely identified study participant regarding the initial EPT readings (treated tooth and control), the amount of time taken to reach both soft tissue and pulpal anesthesia, and the conditions that lead to a "failed" profoundness of anesthesia
  - a. A trained research assistant will separately record each patient's unique identifying code with the anesthetic formulation (buffered vs. unbuffered) that was prepared and administered

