**3.0      Outcome Measures/Endpoints**

**3.1      Primary Outcome Measures**

**3.1.1** The primary outcome is to gauge the time it takes for the buffered anesthetic to provide profound anesthesia, displayed by an EPT reading of 80. The time will be censored at 15 minutes if profound anesthesia is not achieved within 15 minutes.

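### The primary event is EPT=80 alone in Section 3.1.1, but Section 7.0 steps 8a to 9a bring in soft-tissue sensation, so the same patient can be an early event or a failure censored at 15 minutes

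*Combined protocol and SAP*

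**What the plan says.** - **Section 3.1.1 (primary outcome).** The event is the time for the anesthetic to "provide profound anesthesia, displayed by an EPT reading of 80". On censoring: "The time will be censored at 15 minutes if profound anesthesia is not achieved within 15 minutes". Soft tissue is not mentioned.
- **Section 5.0.** The same criterion, EPT alone: "with a reading of 80 showing the tooth is adequately anesthetized".
- **Section 7.0, step 8.** EPT and soft tissue are both assessed at 3 minutes. Under step 8a, EPT=80 "without pulpal or soft tissue sensations indicates profound pulpal anesthesia", and access may then start. Step 8b (wait longer) is written only for EPT not equal to 80.
- **Step 9.** "Retest the tooth being treated using EPT at 2-minute intervals until EPT=80 or when 15 minutes have passed". Soft tissue is not part of the stopping rule, and no further soft-tissue check is scheduled.
- **Step 9a.** "Participants who did not demonstrate total soft tissue and/or pulpal anesthesia within 15 minutes will be categorized as a failure", with time censored at 15 minutes.
- **Step 10.** Pain on access or pulpotomy after EPT=80 is also a failure.
- **Step 11.** The times to soft-tissue and to pulpal anesthesia are both charted.
- **Sections 3.2.1 and 11.0.** They refer to failure of profound (pulpal) anesthesia without saying whether soft tissue counts.

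**The concern.** The primary event has two definitions, and they part company for one kind of patient: EPT has reached 80 but some soft-tissue sensation remains. The choice between them feeds the log-rank and Cox analyses of time, and the chi-square and logistic analyses of failure. For the time analysis the two results are far apart, since the event can fall as early as the 3-minute reading while the alternative is censoring at 15 minutes. With no rule written down, the student researcher who charts the outcome decides case by case, or the choice is made once data have been seen.

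**Working it through.** **1. The patient under each rule (EPT=80, soft-tissue sensation present)**

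| Rule | Result |
|---|---|
| Section 3.1.1, Section 5.0 | Event at that reading |
| Step 8a | Not met, because sensation is present |
| Step 8b | Not met, because EPT is 80 |
| Step 9 | EPT retesting ends |
| Step 9a, *and/or* read as *or* | Failure, censored at 15 minutes |
| Step 9a, both must be lacking | Not a failure |

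The mirror case (EPT not 80, no sensation) also falls outside 8a and 8b, but step 9 keeps retesting that patient.

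**2. The plan's own figure.** Inputs from Section 11.0: hazard ratio 2.25, two-sided 5%, 80% power, control median 10 minutes, 28 per group.
- Freedman events: (1.960 + 0.842)² × (3.25/1.25)² = 7.849 × 6.76 = 53.06, rounded up to 54. That is 27 per group if every patient has the event, close to the stated 28.
- With censoring at 15 minutes and exponential times, λ = ln 2/10 = 0.0693. The event probability is 1 − exp(−0.0693 × 15) = 0.646 for control and 1 − exp(−0.0693 × 2.25 × 15) = 0.904 for buffered.
- Expected events: 28 × (0.646 + 0.904) = 43.4.
- Schoenfeld power: Φ(√43.4 × ln 2.25/2 − 1.960) = Φ(0.71) = 76%.

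The baseline below is therefore about 77% (simulated) and not 80%. That gap comes from the 15-minute censoring and is a separate matter.

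**3. Failure proportions.** Let s be the share of EPT=80 patients recoded as failures, equal in both arms. The documents give no value, so s is an assumption. Failure = 1 − p(1 − s).

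| s | Patients recoded (43.4 × s) | Control | Buffered |
|---|---|---|---|
| 0 | 0 | 35% | 10% |
| 5% | 2.2 | 39% | 14% |
| 10% | 4.3 | 42% | 19% |
| 20% | 8.7 | 48% | 28% |

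**4. Log-rank power.** Simulated trials, 3,000 to 4,000 per scenario: 28 per arm, exponential times, hazard ratio 2.25, readings at 3, 5, …, 15 minutes. Power with EPT=80 alone as the event is about 77%. The delayed columns let soft tissue become numb 2 or 4 minutes after EPT=80 and move the event to that reading. *Disagree* is the percentage of trials in which the two codings differ on significance.

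| s | Sensation to 15 min: power | Disagree | 2-min delay: power | Disagree | 4-min delay: power |
|---|---|---|---|---|---|
| 5% | 67% | 14% | 76% | 2% | 76% |
| 10% | 58% | 24% | 77% | 3% | 75% |
| 20% | 43% | 38% | 77% | 4% | 74% |

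Across the delayed runs as a whole, disagreement was about 1-7%.

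**5. Type I error.** At hazard ratio 1, rejection stayed at about 4-6% under every coding.

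**The case against.** The strongest reply is that the documents lean toward an answer. Section 3.1.1 is the endpoint section and names EPT=80, Section 5.0 agrees, and Section 11.0 speaks of pulpal anesthesia. On that view step 8a governs when treatment starts, not the endpoint. This is a good reason for choosing EPT=80 in the fix, but it does not remove the conflict: step 9a sets failure and censoring for the analysis, and it names soft tissue.

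Four stronger readings might be inferred, and the documents do not support them.

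- *The patient can never be reassessed.* Step 9 ends EPT retesting only. It does not bar a later soft-tissue check, and step 11 implies one, since it charts a time for soft tissue as well as pulp. What is missing is a schedule.
- *Step 9a certainly makes this patient a failure.* Its *and/or* can also mean that both must be lacking.
- *Even a small share moves the result materially.* That holds only if sensation persists to 15 minutes. With a delay of 2 to 4 minutes the effect is slight. The documents give neither the share nor the persistence.
- *The conflict favors one arm or manufactures an effect.* With an equal share, both arms lose the same proportion of events. The buffered arm loses more in absolute points (90% to 81%, against 65% to 58%, at s = 10%) only because more of its patients reach EPT=80. The cost is power, not false positives.

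**Conclusion.** The inconsistency stands on the text, whatever the share of affected patients. Sections 3.1.1 and 5.0 on one side, and steps 8a and 9a on the other, can give the same patient different primary and failure outcomes, and neither Section 3.2.1 nor Section 11.0 settles it. Its size is unknown. It runs from almost nothing, if soft tissue follows the pulp within 2 to 4 minutes, to a loss of about 10, 19 and 34 percentage points of power at shares of 5%, 10% and 20% (77 − 67, 77 − 58, 77 − 43), if sensation lasts to 15 minutes. These figures assume exponential times, the planned hazard ratio and an equal share in both arms. The larger ones are an extreme case and should not be quoted as the expected effect. A primary event still needs one definition, fixed before unblinding.

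**What to change.** For analysis, carry the Section 3.1.1 definition through Sections 3.1.1, 7.0 (steps 8a, 8b, 9 and 9a) and 11.0:

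- **Time outcome.** Event time is the first EPT=80 on the study tooth, censored at 15 minutes if that is not reached. Soft-tissue sensation changes neither the event nor the censoring.
- **Failure outcome (Sections 3.2.1 and 11.0).** Failure is no EPT=80 by 15 minutes, or pain on access or pulpotomy under step 10. Stating both parts keeps the step 10 failures. Because Section 11.0 ties censoring to failure, it should say that only the first part is censored at 15 minutes. A step 10 failure keeps its event time.
- **Soft-tissue time (step 11).** Report it descriptively only, unless a soft-tissue check is recorded at each reading.

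The passages on when access may begin and when further waiting is needed must be reconciled by the sponsor. No clinical rule is proposed here.

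The cost is wording in Sections 3, 7.0 and 11.0, with no added patients. New data are needed only if soft-tissue time is to be analyzed formally, since no soft-tissue check is scheduled after 3 minutes.

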### **1.0 Background & Rationale**

---

The success rate for pulpal anesthesia in mandibular molars diagnosed with symptomatic irreversible pulpitis has been shown to be between 45-70% (1). While the specific mechanism for inadequacy is unknown, it has been proposed that expression of variable sodium channels during inflammation, changes in tissue pH and, peripheral blood flow may contribute (2). OnPharmaTM offers a solution to increase the efficacy of local anesthetics by allowing the clinician to add a buffering agent to the solution prior to injection.

The OnPharmaTM system adds sodium bicarbonate to the anesthetic solution to raise its pH to a level closer to the anesthetics pKa. In doing so, more of the free base form is present to

diffuse through cell membranes. The free base is the active ingredient in local anesthetic solutions that are responsible for analgesia. In addition, CO2 and water are produced through the addition of sodium bicarbonate to the anesthetic solution. CO2 converts the local anesthetic back into its active acid form once inside the cell membrane, trapping the local anesthetic inside (2,3).

Recent studies have suggested that buffered anesthetics do not improve Inferior alveolar nerve block (IANB) success rate in symptomatic teeth (4,5,6). This contrasts with another study showing increased success with sodium bicarbonate use with IANB blocks (7). While the field is not currently in agreement, Indiana University School of Dentistry (IUSD) has had a positive experience when using the OnPharmaTM system to anesthetize symptomatic teeth.

[name], a previous resident of Indiana University Endodontics, investigated the efficacy of buffered and plain 2% lidocaine with 1:100k epinephrine. His data suggest that there is not a significant difference between the two when treating mandibular molars diagnosed with symptomatic irreversible pulpitis. This current iteration aims to investigate the synergistic ability of a combination of buffered anesthetics to improve patient analgesia. Previous studies have reported that a local infiltration of articaine with a IANB of lidocaine improve local anesthetic success rates in patients diagnosed with symptomatic irreversible pulps (8,9). Carbocaine performs as well as lidocaine when used solely for an IANB but current data suggests it does not improve anesthesia when combined with other anesthetics (10,11).

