### **4.2 Exclusion Criteria**

- Patients lacking a response to cold in the affected tooth
- A radiographic periradicular pathosis more advanced than a widened periodontal ligament (radiograph taken as standard of care)
- No vital coronal pulp tissue noted upon access
- Patient reported pain (other than pressure) upon endodontic access/pulpotomy

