## **11.0 Statistical Considerations**

The two groups will be compared for differences in the percentage of subjects who fail to achieve profound pulpal anesthesia using chi-square tests. The time needed to achieve profound pulpal anesthesia for the two groups will be compared using Kaplan-Meier survival curves and log-rank tests, with patients who fail to achieve profound pulpal anesthesia censored at 15 minutes. A logistic regression model for presence of profound pulpal anesthesia will be used to determine whether molar type (first, second, third molar) affects the group comparisons; the model will include both factors and their interaction. A similar Cox proportional hazards survival model will be used for the analysis of time needed to achieve profound pulpal anesthesia. VAS scores will be compared between treatments using a Wilcoxon Rank Sum test. A two-sided 5% significance level will be used for all tests.

With a sample size of 28 subjects per group, the study will have 80% power to detect a hazard ratio of 2.25 between the two groups for time to profound pulpal anesthesia, using calculations with a two-sided 5% significance level and based on a log-rank test with median time to anesthesia 10 minutes in the control group. Sample size calculations were performed using PASS 2019 (NCSS, LLC. Kaysville, UT). To account for up to 2 subjects per group with unusable data, the study will enroll 30 subjects per group.

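### The planned VAS comparison can include only patients who reached anesthesia, a post-randomization result that buffering is meant to change, and Section 11.0 does not say so.

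*Combined protocol and SAP*

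**What the plan says.** Section 7.0 sets the order of events. Step 5 is "Randomize the subject to the type of anesthetic formulation". After the injections the tooth is tested by EPT up to 15 minutes. Patients without anesthesia by then are failures under step 9a, and the plan continues: "No additional study outcomes will be collected from the patients, who will be withdrawn from the study". They then receive supplementary anesthesia outside the study.

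Step 10 deals with patients who reach EPT 80 but feel pain at access or pulpotomy. They "will also be categorized as a failure (lack of anesthetic profoundness), withdrawn from the study". Item 10a, printed beneath that step, says that the VAS "will be used to report the patient's perceived discomfort at the end of treatment". Section 4.2 lists the same event as an exclusion criterion: "Patient reported pain (other than pressure) upon endodontic access/pulpotomy".

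Failure and VAS are both secondary outcomes (3.2.1 and 3.2.2). Section 11.0 tests failure by chi-square, and for pain it states: "VAS scores will be compared between treatments using a Wilcoxon Rank Sum test". It names no analysis set for VAS, no rule for patients who failed, and no qualification of the result.

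**The concern.** A step 9a failure leaves the study before the VAS is taken, so following the plan as written gives a Wilcoxon test on successes only. Success is a result of the assigned treatment, and the primary objective (2.1.1) is to find out whether buffering makes anesthesia faster and more profound. The better buffering works, the more unequally the two VAS groups are selected.

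Suppose that buffering rescues patients who would otherwise have failed, and that such patients tend to report more pain. The buffered group then keeps painful patients whom the control group has lost. Buffering could reduce failure and still appear to worsen pain, with nothing in Section 11.0 to warn the reader that the VAS groups are no longer the randomized groups.

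**Working it through.** **Inputs.** From Section 11.0: "median time to anesthesia 10 minutes in the control group", hazard ratio 2.25, two-sided 5%, 28 per group for analysis and 30 enrolled. From 3.1.1: censoring at 15 minutes. The shape of the time distribution and the link between failure and pain are not in the documents and are assumed below.

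**1. The plan's own figure.** Freedman's formula gives (1.960 + 0.842)² × (3.25/1.25)² = 7.85 × 6.76 = 53.1, taken as 54 events. That is 27 per group if every patient has an event, against 28 stated. The match ignores the 15-minute censoring. That is a separate matter, and nothing below depends on it.

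**2. How many patients can have a VAS.** With a Weibull curve of shape k that keeps the stated median and hazard ratio, success by 15 minutes is 1 − 0.5^(1.5^k) in control and 1 − 0.5^(2.25 × 1.5^k) with buffering. Shape 1 is the exponential.

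| Shape k | Success, control vs buffered | Expected VAS of 30, control vs buffered |
|---|---|---|
| 1 | 64.6% vs 90.4% | 19.4 vs 27.1 |
| 1.5 | 72.0% vs 94.3% | 21.6 vs 28.3 |
| 2 | 79.0% vs 97.0% | 23.7 vs 29.1 |
| 3 | 90.4% vs 99.5% | 27.1 vs 29.8 |

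These are expected counts before any losses at step 10. The plan's inputs do not fix the shape, so they do not fix the split.

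**3. What the selection could do to the test (illustration).** Each patient has a resistance to anesthesia and a pain score, jointly normal with correlation ρ in both arms. The patient succeeds if resistance is below the arm's threshold. Buffering has no effect on pain. Trials have 30 per arm, and successes are compared by a two-sided 5% Wilcoxon test. The figure is the percentage of trials that are significant against buffering (nominal 2.5%).

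- Exponential times, hazard ratio 2.25, ρ = 0, 0.3, 0.5, 0.7: 2.6, 5.5, 9.2, 15.4%.
- ρ = 0.5, Weibull shape 1.5, 2, 3: 8.1, 7.0, 4.3%.
- ρ = 0.5, exponential, with the most painful 10% or 20% also giving no VAS because of step 10 (assumed): 7.1% (18.6 vs 25.0 patients with VAS) or 5.7% (17.2 vs 22.6).
- Hazard ratio 1.5, ρ = 0.3, exponential: 3.8%.
- No effect of buffering on failure: about 2.5%.

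**4. Control success set directly.** Section 1.0 says that anesthetic success in this condition "has been shown to be between 45-70" percent. Buffered success is 1 − (1 − control success)^2.25. With control success of 45% or 70% this is 73.9% or 93.3%, and at ρ = 0.5 wrong-direction significance is 9.3% or 8.8%. With 85% or 90% (assumed, since the regimen adds articaine) it is 6.1% or 4.8%.

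**5. How a worst-rank analysis behaves.** Give every failure the same worst rank, with success 64.6% vs 90.4% and no effect on pain. The Wilcoxon test then favours buffering in about 41% of trials, from failure alone. The uncorrected chi-square test is significant in 69.5%, and both are in 38.2%, so about 93% of the worst-rank results (0.382/0.413) are accompanied by a significant chi-square. With no effect on failure the worst-rank test rejects in 4.9%.

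**The case against.** **Buffering may not change failure.** Section 1.0 cites recent studies in which buffered anesthetics did not improve block success, one study with the opposite result, and in-house data showing no significant difference between buffered and plain lidocaine. The hazard ratio of 2.25 is the effect that the trial is sized to detect, not a forecast. This stands as a limit on the likely bias. It does not remove the point: the combined buffered regimen is the question under study, and the analysis must be interpretable if buffering works.

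**The link between failure and pain is unknown.** This also stands. With modest inputs little happens: at hazard ratio 1.5 and ρ = 0.3, rejections total 3.8 + 1.7 = 5.5% against 5%. A reader might infer that the VAS test is bound to be biased against buffering. That needs both a lower failure rate with buffering and a positive failure-pain link, and the documents establish neither.

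**Stopping VAS at failure is defensible.** A later score would follow the supplementary injections that step 9a provides for. Agreed: the point is how the remaining scores are analysed and described, not that VAS should be collected after failure.

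**Step 10 patients.** A reader might infer that patients with pain at access have no VAS either. Step 10 withdraws them and Section 4.2 excludes them, but item 10a sits beneath that step. The scales that item 10a refers to are not visible in the text available and may settle it. Step 9a is explicit whatever the answer.

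**It is only a secondary outcome.** True, and no power is claimed for it. It still carries a stated between-arm test at two-sided 5%.

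**Conclusion.** The point holds as a flaw in a stated secondary analysis. Step 9a removes VAS for every 15-minute failure, and Section 11.0 then compares VAS between arms as if the groups were still those randomized. This follows from the text and needs no assumption.

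The size does need assumptions. At the design inputs VAS would exist for about 19 vs 27 of 30 (exponential), or about 22 vs 28 to 27 vs 30 (Weibull shapes 1.5 to 3), before step 10 losses. Wrong-direction significance is illustrative only: about 4 to 9% at correlation 0.5 across these shapes, just under 4% at hazard ratio 1.5 with correlation 0.3, and the nominal 2.5% if buffering does not lower failure or failure is unrelated to pain.

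A reader might extend this to the primary result. The documents do not support that: step 9a failures stay in the log-rank analysis, censored at 15 minutes, and they are counted in the chi-square test. Whether step 10 failures stay in the chi-square test depends on how Section 4.2 is applied, which is a reason to reconcile the text and not part of the size given here.

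**What to change.** In Section 11.0:

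1. Define the VAS analysis set as patients with successful anesthesia, meaning neither a step 9a nor a step 10 failure. Label the result, and any p-value, as conditional on success and not a randomized comparison. Show failure rates by arm beside it. Dropping the p-value altogether is a matter of preference and is not required.
2. Add, as a sensitivity analysis only, a Wilcoxon test on all randomized, treated patients with every failure given the same worst rank. State that it is a composite of failure and pain that overlaps with the chi-square test, and that it must not be read as a pain result.
3. Reconcile Section 4.2 with steps 10 and 10a, so that pain at access after randomization is analysed as a failure, as step 10 already says, and does not remove the patient from the failure analysis. State whether these patients give a VAS.

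The cost is a short paragraph in Section 11.0 and consistent wording in Sections 4.2 and 7.0. Items 1 and 2 need no new data, because step 11 already charts the conditions that lead to failure. The downsides are that the VAS result becomes weaker evidence and that a little more analysis is needed.

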**3.2      Secondary Outcome Measures**

**3.2.1** Failure to achieve profound anesthesia.

**3.2.2** Pain scores measured using a Visual Analog Scale (VAS).

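### The only VAS is taken at the end of treatment, so in patients who hurt on access the severity of pain under the study anesthetic is blurred by rescue or not recorded

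*Combined protocol and SAP*

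**What the plan says.** Section 3.2.2 names VAS pain scores as a secondary outcome. It gives no time point, no period to be rated and no population. The only timing is in Section 7.0, step 10a: "Visual Analog Scales (VAS) shown below will be used to report the patient's perceived discomfort at the end of treatment".

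Step 10, to which 10a belongs, deals with patients who had reached EPT = 80 and then report "any pain (excluding pressure) elicited from the tooth undergoing treatment upon endodontic access or a complete pulpotomy". They are classed as failures, "withdrawn from the study, and appropriately managed as previously described". The description referred to is in step 9a, for patients not anesthetized by 15 minutes: "further managed according to the best clinical practice (additional block/supplementary injections) so that the endodontic treatment may continue appropriately". Step 9a also says of those 15-minute failures: "No additional study outcomes will be collected from the patients, who will be withdrawn from the study". Step 10 has no equivalent sentence.

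Section 4.2 lists pain on access or pulpotomy among the exclusion criteria, although it can only be observed after randomization.

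Section 11.0 states the analysis: "VAS scores will be compared between treatments using a Wilcoxon Rank Sum test". It has no rule for patients who were rescued, withdrawn or left without a score.

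**The concern.** Access and pulpotomy are where the study anesthetic is put to the test. Step 10 asks about pain at that moment, but the graded scale is used only once the procedure is over. For a patient in whom the study anesthetic proved inadequate, two things happen in between: further anesthetic is given and the treatment is completed. A score of current discomfort then describes the study anesthetic plus the rescue, not the study anesthetic alone.

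If the word *withdrawn* means that no score is taken, the same patients drop out of the comparison, and they drop out because of their outcome. The arm with more access pain loses more of its high scores. A finding of no VAS difference would then say little about whether buffering reduces the severity of pain on access.

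**Working it through.** **1. Order of events in Section 7.0.**

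| Patient | What happens before the end of treatment | VAS under the plan |
|---|---|---|
| Not anesthetized by 15 min (step 9a) | Withdrawn, supplementary anesthesia | None; no further outcomes |
| EPT = 80, pain on access or pulpotomy (step 10) | Withdrawn, supplementary anesthesia | Unclear: 10a sits under step 10, which suggests a score; withdrawal and the Section 4.2 exclusion suggest none |
| EPT = 80, no access pain | No rescue described | Scored under the study anesthetic alone |

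The point concerns the second row. Its score is post-rescue, a recall of mixed phases, or missing. No reading of the text gives a score marked before rescue.

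**2. How many patients reach access.** The plan gives no figure for the VAS. Its only sample-size statement (28 per group, 80% power, hazard ratio 2.25, control median 10 minutes) concerns time to anesthesia. It reproduces at 80.4% with the Lachin-Foulkes exponential formula if the 15-minute censoring is ignored. Whether that is adequate is a separate question; here I borrow only the median and the hazard ratio and assume exponential times.

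- Control: 1 − 0.5^(15/10) = 1 − 0.5^1.5 = 0.646; × 30 = 19.4, about 19 patients.
- Buffered: 1 − 0.5^(2.25 × 15/10) = 1 − 0.5^3.375 = 0.904; × 30 = 27.1, about 27 patients.

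**3. What the timing does to the Wilcoxon test.** The documents give no access-pain rate and no VAS distribution, so the following are assumptions: a 0–100 scale, mean 50 (SD 20) for a patient in pain on access, and mean about 5 otherwise. Simulated two-sided 5% Wilcoxon tests, 19 vs 27 patients:

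| Assumed access pain, control vs buffered | Expected patients in pain | Power if scored at access, before rescue | Rejection rate if rescue removes the pain, or these patients are dropped |
|---|---|---|---|
| 50% vs 10% | 9.5 vs 2.7 | about 62% | about 4–6% |
| 40% vs 10% | 7.6 vs 2.7 | about 40% | about 4–6% |
| 30% vs 10% | 5.7 vs 2.7 | about 22% | about 4–6% |
| 30% vs 20% | 5.7 vs 5.4 | about 9% | about 4–6% |

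(Expected counts are 19 or 27 times the assumed rate.)

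Intermediate cases at 50% vs 10%:
- If the end-of-treatment score is a recall that pulls painful scores from a mean of 50 down to 35, power is about 51%.
- If rescue lowers painful scores only to a mean of 20, power is about 24% to 47%, depending on the assumed spread.

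**4. Sensitivity to the assumed scores.** A second set of assumptions (in pain: mean 60, SD 20; not in pain: mean 10, SD 8; after rescue: mean 12, SD 10; numbers reaching access drawn at random) gives about 21% at 30% vs 10%, 21% at 40% vs 20% and 41% at 50% vs 20% when scored at access. In each case the rate is about 5% when scored after rescue and 4–5% when these patients are left out. The direction is the same; the size moves with the assumptions.

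**The case against.** A reader might infer that the VAS endpoint as a whole fails to measure pain under the study anesthetic, and that any benefit of buffering on pain would be hidden. The documents do not support that, for four reasons.

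- **Patients without access pain are unaffected.** No rescue is described for them. They may also report discomfort from later in the root canal, which an end-of-treatment score can legitimately capture. This stands and limits the point to patients who hurt on access.
- **The rating may be a recall of the whole procedure.** The wording of step 10a allows it, and the scale, which might settle it, is a figure not reproduced in the available text. Undiminished recall would cost no power. This stands as an uncertainty. But the rating would still be made after rescue, and the text does not say which period is to be rated.
- **The rescued score may never enter the test.** If withdrawn patients give no VAS, there is no contamination. That is correct, but the problem then becomes selection after randomization of patients without access pain, and the power results in that case are no better.
- **Access pain is recorded elsewhere.** Step 10 counts it as failure before rescue, and failure is outcome 3.2.1, compared by chi-square. This stands, subject to the conflict with the Section 4.2 exclusion. What is lost is severity, not occurrence.

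It is also fair that the trial is not powered on the VAS. At 30% vs 20% access pain, scoring at access still gives only about 9% power, so re-timing does not guarantee an informative test.

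**Conclusion.** The point holds within these limits. As written, the plan gives patients who hurt on access a VAS that is post-rescue, a mixed recall, or absent, and these patients carry most of the information on an arm difference in pain severity. Only the VAS comparison is affected; the time-to-anesthesia analysis is not.

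The loss ranges from nothing (undiminished recall) to all of the available power (about 62% down to about 5% at 50% vs 10% access pain). Where the access-pain rates differ little, there is not much power to lose. These sizes depend on assumed access-pain rates and VAS distributions, and on the plan's own median and hazard ratio with exponential times. The order of events does not depend on them. This is worth correcting before enrollment, as an improvement to a tested secondary endpoint.

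**What to change.** 1. In Section 3.2.2 and step 10a, define the VAS endpoint as pain during access or pulpotomy under the study anesthetic.
2. Record it from every patient who enters access, including step 10 failures: at the first report of pain and before any supplementary injection, or on completion of the pulpotomy if no pain is reported.
3. In Section 11.0, use this score in the Wilcoxon test. Keep any end-of-treatment VAS as descriptive, and state what period it rates.
4. Reconcile steps 10 and 10a with the Section 4.2 exclusion, so that access-pain failures stay in the VAS analysis.

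The cost is protocol wording and a brief pause for the patient to mark the same scale, with no added staff or equipment. Clinical management is otherwise unchanged. The change does not supply a VAS for patients not anesthetized by 15 minutes (about 30 − 19 = 11 control and 30 − 27 = 3 buffered on the plan's own figures); that gap is separate.
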